4.1. Investigational Agent

Heplisav B

4.2. Preclinical Data

Included in Investigator's Brochure [Feb, 2019, revision 16].

4.3. Risk/Benefits of Study

The risk benefit ratio for this study is considered to be low to moderate only. There are several reasons for this presumed level of risk. Acute myocardial infarction was reported in 19 patients, as compared with 3 patients taking the traditional vaccine. Additional evidence, however, considering the presence of risk factors does not support a clear cause and effect relationship. The risk of immune mediated events with Heplisav B appears to be very low. The results of multiple phase III studies which included more than 5,000 non-infected immune competent patients have shown that it is not associated with a disproportionate amount of immune events, including the origination of what are commonly considered to be autoimmune disorders or potentially immune-mediate medical conditions (piMMCs). In those few situations where immune mediated disorders appeared to arise after vaccination, an outside panel of experts did not attribute them to vaccination. Also, Heplisav-B vaccination was not associated with an unusual frequency of ANA or anti-ds-DNA antibodies. Certain relatively common immunologic disorders such as juvenile diabetes, hypo or hyperthyroidism, and rheumatoid arthritis were not more common when compared with those given traditional vaccine. One reason for this may be that the 1018-HBsAg adjuvant is not anticipated to promote innate immunity to host tissue proteins because TLR activation is primarily a defense mechanism against infecting microbes rather than host tissue antigens. Also, it has been proposed that the 1018 adjuvant stimulates a directed immune response to HBsAg instead of the multi-pathway, broad immunostimulatory response induced by alum adjuvant [Investigator's Brochure, February 2019, revision 16].

Patients receiving chemotherapy are not anticipated to have an unusual frequency of adverse effects to the vaccine. In this study it is anticipated that all HBsAg negative, anti-HBc positive cancer patients will be placed on the standard of care antiviral prophylaxis which greatly minimizes the chances for HBV reactivation (HBVr). Thus, HBVr is very unlikely to interrupt the study. Should the vaccine prove to be highly immunogenic in cancer patients, rapid induction of seroprotective anti-HBs could further reduce the risk of HBVr.

The risk for acute cellular rejection of the liver should be minimal because this requires an orchestrated T lymphocyte response to alloantigens expressed on the surface of liver cells. Moreover, transplanted patients will have had remote transplantation (> 3 years) and are much less likely to undergo acute cellular rejection. Should the vaccine be highly immunogenic in these patients, it might eliminate the need for the very costly hepatitis B immune globulin (HBIg) immunoprophylaxis and ultimately might decrease the need for life-long antiviral prophylaxis after transplantation for hepatitis B. As with anti-HBc-positive cancer patients, all patients transplanted for hepatitis B and those given an anti-HBc positive liver organ will receive the standard of care antiviral prophylaxis to recurrent hepatitis B and de novo infection, respectively.

A third dose of the vaccine is unlikely to result in adverse events. This has been given to several hundred hemodialysis patients in phase III studies and there were no disproportionate adverse event outcomes when compared to historical cohorts who were administered four doses of Engerix [Investigator's Brochure, Feb 2019, version 16].

Potential benefit. If seroprotective levels of anti-HBs are demonstrated in medically immunosuppressed individuals, the potential benefit to society could be very large. For example, there are more than 3 million people in the US who are taking long term biologic immunosuppressive therapy for chronic inflammatory disorders and with a population prevalence for anti-HBc alone of 5 percent, this could reduce the need to depend on potentially life-long antiviral prophylaxis in 100,000 to 150,000 cases. This same figure of 5% prevalence of anti-HBc in the general population can be applied to individuals undergoing chemotherapy for malignancy (estimated incidence of 68,760 anti-HBc positive cases undergo chemotherapy in the United States each year). ²¹ Long term antiviral prophylaxis may be associated with unanticipated adverse events and is economically costly. Taken together, approximately 5 to 8% of all adults transplanted require antiviral therapy either to prevent recurrent hepatitis B or to prevent de novo infection.

4.4. Dose Rationale

The standard 0.5 ml dose of Heplisav-B will be delivered at baseline (0 time) and 4 weeks later. Immunologic efficacy will be compared to historical cohorts in phase III trials of the vaccine. In the event that a seroprotective level of anti-HBs (< 10 mlU/ml) does not develop by week 8, a booster dose of Heplisav-B vaccine will be given at week 12.

4.5. Trial Conduct

This study will be conducted in compliance with the protocol approved by the Institutional Review Board, and according to Good Clinical Practice standards. No deviation from the protocol will be implemented without the prior review and approval of the IRB except where it may be necessary to eliminate an immediate hazard to a research subject. In such case, the deviation will be reported to the IRB as soon as possible.

4.6. Population

This is an exploratory observational study of 18 individuals divided into 3 equal sized groups of six patients (Groups A, B, and C). Groups A (chronic inflammatory disorders) and B (patients on cancer chemotherapy for solid organ malignancy) will be limited to patients with resolved hepatitis B as defined by the absence of HBsAg and the presence of anti-HBc in serum. Patients who have low titer anti-HBs at baseline (< 20 mIU) will not be excluded. Group C (liver transplant) patients will be HBsAg negative and anti-HBc positive after transplantation for hepatitis B or seronegative for all HBV markers if a recipient of an anti-HBc positive donor organ.

4.7. Schedule of Events

The schedule of events can be seen in Table 1. Patients will be seen and consented at a screening visit to determine eligibility. It is anticipated that most if not all of the serologic data needed to qualify the patient will be available by review of electronic records at the screening visit. If not, one or more of the serologic HBV markers will be tested at screening. The serologic studies for HBV must have been done within the past year. Turnaround times are less than 5 days and so there should be no lagging data needed at the time the patients receive their first dose of vaccine 28-30 days later. There will also be a 28-30 day window between the first vaccine inoculation visit and the second vaccine inoculation visit. The 12, 24, and week 60 visits will have a one week \pm window.

In the event of an intercurrent acute illness that either places the patient at added risk or makes vaccine adverse event relatedness difficult to interpret, every effort will be made to bring the patient back when the illness is resolved and preferably no longer than one week of the initially specified time.

Heplisav-B vaccine will be delivered at the baseline/enrollment visit (visit # 2 considered to be day 0) and again 4 weeks later. In the unlikely event that anti-HBs titer is ≥ 300 mIU/mI after a single dose of vaccine, patients will not be given a second dose. All individuals who do not have protective levels of anti-HBs (> 10 mIU/mI) after two doses at week 8 will be given a third identical dose of vaccine at the week 12 visit.

Adverse events (e.g, localized skin reactions, fever) that occur soon after vaccination will be assessed by weekly telephone assessments and patients will be asked to record changes in underlying disease activity on a Patient Related Outcome Measurement form. These will be distributed at the enrollment visit and subsequent visits. They will initially be completed by the patient and completed as needed by the investigator and coordinators at all study visits. Data on all AEs will be recorded on an Adverse Event Data Capture form (Appendix 1). These will be filled out by the study coordinator in conjunction with the investigator at each visit.

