Schedule of Events:	In the absence of appropriate documentation, all patients will initially be screened for HBsAg, anti-HBc, and anti-HBs status by qualitative testing at a screening visit. Patients in Group A and B found to be anti-HBs positive will be tested for anti-HBs quant within one week to confirm final eligibility. Two doses of Heplisav-B will be administered at a baseline visit and 4 weeks later. Anti-HBs levels will be assessed at the baseline visit and again at weeks 4, 8, 12, 24 and 60. All patients who fail to respond with seroprotective anti-HBs levels (≥ 10 mIU/mL) at week 8 will be given a third dose of vaccine at week 12 and followed until week 60. Liver transplant patients (Group C) will be vaccinated and followed in the same manner as Groups A and B.

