after liver transplantation. The proposed study is the first known to the investigator in which patients are administered HBsAg-1018 containing vaccine immediately before or during ISDT. It is also the first to use this vaccine in persons with serologic evidence for resolved hepatitis B. However, vaccinating anti-HBc positive patients who are taking ISDT can be justified by previously published studies. First, as many as 40% of patients with the serologic profile of resolved hepatitis have seroprotective levels of anti-HBs due to the fact that exposure to HBV may have occurred remotely in the past. Second, an anamnestic boost in anti-HBs has been reported in a substantial minority of immunocompetent anti-HBc positive individuals after a single dose of traditional HBV vaccine. In consideration of these findings, the current study will not exclude anti-HBc positive patients who have weak anti-HBs levels (<20 mIU/ml). Third, the medical literature supports a lower frequency of HBVr in anti-HBs positive individuals over a broad range of ISDTs. Pourth, some studies using quantitative anti-HBs assays have reported greater protection against HBVr in persons having a high anti-HBs titer compared to individuals with low titer or no detectable anti-HBs.

Heplisav-B vaccine has been shown to more quickly result in seroprotective levels of anti-HBs and higher geometric mean titers than traditional HBV vaccine in immunocompetent recipients including the elderly, persons with diabetes mellitus, and patients with chronic kidney failure. These are important groups to have studied because It can be anticipated that some recipients may have had age or disease-related subclinical immune deficiency.

Use of Heplisav-B in patients with prior hepatitis B (Groups A and B).

Prevention of HBVr.

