7.2. Exclusion Criteria

- 1.) HBsAg positivity
- 2.) Anti-HBs titer ≥ 20 mIU/mL at baseline
- 3.) HIV infection**
- 4.) HCV infection**
- 5.) Prior hepatitis B vaccination
- 6.) Receipt of hepatitis B immune globulin during the past 4 months
- 7.) Hematologic malignancy

- 8.) Hepatocellular carcinoma
- 9.) Active alcohol use > 20 grams daily
- 10.) Unstable underlying inflammatory disorder
- 11.) Pregnancy or breast feeding
- 12.) History of severe depression or other severe psychiatric disorder
- 13.) Receipt of liver allograft < 3 years earlier
- 14.) Transplant rejection within the past year
- 15) Individuals having unstable or poorly responsive inflammatory disorders
- 16) All persons who are judged by the investigator to have an unreasonable risk of complications
- 17) Anticipated life expectancy less than one year

Footnotes to Inclusion/Exclusion Criteria *There must be evidence of anti-HBc positivity at the screening visit and if so, documentation that this is chronic in nature will be obtained from a review of the electronic record (for example, history of past exposure, past serology documentations). If documentation is lacking, however, then an IgM anti-HBc test will be at done at the screening visit to confirm that the patient has not recently acquired hepatitis B.

**Serologic testing for HCV and HIV must be within 4 months of potential eligibility. If this is not the case, the testing will be repeated at the screening visit.

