^{** 5%} of recipients of anti-HBc donor liver are anticipated to be anti-HBc positive. These patients will be excluded if anti-HBs also > 20 mIU/ml. Patients transplanted for HBV infection are anticipated to be anti-HBc positive

[#] If anti-HBs level remains < 10 mIU/ml

TABLE 1. Study Participation Table

	Visit 1: Screening	Visit 2 Enrollment/ Baseline	Visit 3 4 Week Follow up (+/- 3-5 d)	Visit 4 8 Week Follow up (+/- 3-5 d)	Visit 5: 12 Week Follow Up (+/- 3-5 d)	Visit 6: 24 Week Follow Up (+/- 1 week)	Visit 7: 60 Week Follow Up (+/- 1 week)
Read and Sign Informed Consent	Х						
Medical History	Х						Х
Review of Immunosuppresants	Х	Х	Х	Х	Х	Х	Х
Interview, brief physical	Х	Х	Х	Х	Х	Х	Х
Vital Signs (heart rate, blood pressure, temperature)	Х	Х	Х	Х	Х	Х	Х
Missing HBV blood testing*	Х						
Quant anti-HBs	X [≠]	Х	Х	Х	Х	Х	Х
CRP**		Х	Х	Х	Х	Х	Х
Pregnancy test [¥]	Х	Х	Х		Х	X _∞	
Hepatic function panel		Х	Х	Х	Х	Х	Х
Patient Related Outcome Form for Inflammatory Disorder		Х	Х	Х	Х	Х	Х
Repository Blood Sample (for repeat antibody test)		Х	Х	Х	Х	Х	Х
Vaccine Administration, with observation for reactions		Х	Х		X***		
Adverse effects form [±]			Х	Х	Х	Х	Х

^{*} Test for anti-HBs, anti-HBc, or HBsAg if not in the medical record or > one year previously. Test for HIV and HCV antibody is not within 4 months of screening.

[≠] Only done at this visit if medical record indicates patient is anti-HBs positive by qualitative testing.

^{**} This will only be done in patients taking TNF or interleukin inhibitor therapy for chronic inflammatory disorders.

[¥] If potentially child bearing female. Patients who are positive will not be eligible.

^{***} A 3rd dose will be offered to those participants who lack seroprotection (>10 mIU/ml) at week 8.

[±] Observation for adverse events includes weekly telephone calls for 4 weeks after each vaccine dose.

 $[\]infty$ If patient requires third dose of vaccine as per protocol.

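### The section 4.7 rule that omits dose 2 at a titre of 300 mIU/mL or more relies on a sample drawn at the dose-2 visit, so it cannot be applied as scheduled

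*Protocol*

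**What the plan says.** Section 4.7 sets the schedule: "Heplisav-B vaccine will be delivered at the baseline/enrollment visit (visit # 2 considered to be day 0) and again 4 weeks later". It then adds a titre rule. If anti-HBs is at least 300 mIU/mL "after a single dose of vaccine, patients will not be given a second dose". The section calls this event unlikely and does not name the sample that decides it.

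Other places bear on the rule:

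- **Sampling.** The Synopsis and section 9.2 place titres after dose 1 at weeks 4, 8, 12, 24 and 60. None falls between baseline and week 4.
- **Table 1.** The Visit 3 (week 4) column carries both the quantitative anti-HBs and the row "Vaccine Administration, with observation for reactions". The week 12 dose has a footnote making it conditional; the week 4 dose has none.
- **Synopsis.** "Two doses of Heplisav-B will be administered at a baseline visit and 4 weeks later", with no exception. Section 4.4 likewise gives the second dose without condition.
- **Section 6.7.** The list of reasons for withholding further vaccine contains no titre criterion.
- **Turnaround.** Section 4.7, speaking of screening serology, says "Turnaround times are less than 5 days".
- **Windows.** Section 4.7 allows 28-30 days between the first and second doses. Table 1 allows plus or minus 3-5 days around week 4.
- **Comparison.** Section 6.1 compares the endpoints with immunocompetent historical cohorts who had the same Heplisav-B dosing.

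**The concern.** A rule that makes a dose depend on a laboratory result needs that result in hand when the dose is due. Here the deciding sample is taken on the dosing day. Staff must either give dose 2 without knowing the titre, which defeats section 4.7, or hold the dose until the result returns, which the Synopsis and Table 1 do not provide for and which may overrun the interval in section 4.7. Section 4.5 bars unapproved deviations except for an immediate hazard, so staff should not have to improvise.

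The statistical stake is the definition of the regimen. Depending on which passage is followed, a patient with a high week 4 titre may receive one dose or two. That patient then enters a comparison with cohorts described as identically dosed, in groups of only six.

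**Working it through.** The plan states no figure to reproduce. The check compares the time available between sample and dose with the time the assay needs.

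**Inputs.** Dose 1 is day 0 (section 4.7). The only sample between doses is at week 4, day 28 (Synopsis, section 9.2, Table 1). Dose 2 is at the same visit (Table 1). Turnaround is under 5 days (section 4.7). This is stated for screening serology; that it also applies to the week 4 quantitative assay is an assumption.

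**Time available = day of dose 2 minus day of sample.**

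| Reading | Calculation | Days available | Result assured? |
|---|---|---|---|
| Table 1 as written, one visit | 28 - 28 | 0 | Only with a same-day assay, which is not described |
| Section 4.7, interval used in full | 30 - 28 | 2 | No |
| Table 1, dose held to +3 days | 31 - 28 | 3 | No |
| Table 1, dose held to +5 days | 33 - 28 | 5 | Yes, but past the day 30 limit of section 4.7 |

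Holding the dose long enough therefore fits only the wider Table 1 window, and only by splitting a visit that Table 1 shows as one. An earlier draw would also work: a sample on day 28 - 5 = 23 to 28 - 3 = 25 returns by day 23 + 5 = 28 to 25 + 5 = 30. No separate draw of that kind is scheduled.

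**Contrast with dose 3.** That rule uses the week 8 titre for a week 12 dose, a lead of (12 - 8) × 7 = 28 days, and Table 1 marks the dose as conditional. The dose-2 rule has neither feature.

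**Does the baseline exclusion share the fault?** Exclusion 2 in section 7.2 reads "Anti-HBs titer ≥ 20 mIU/mL at baseline", and baseline is the dose-1 visit. However, the Synopsis requires a quantitative titre within one week for Group A and B patients found anti-HBs positive at screening. Table 1 also places a quantitative titre at Visit 1, with the footnote "Only done at this visit if medical record indicates patient is anti-HBs positive by qualitative testing". Seven days plus a turnaround of under 5 days gives a result by about day 7 + 5 = 12 after screening. Dose 1 follows screening by 28-30 days, leaving 28 - 12 = 16 to 30 - 12 = 18 days. For these patients the exclusion can be applied in time. What remains is a wording gap:

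- The criterion says baseline, although the titre that can act before dose 1 is the screening one.
- The confirmation step in the Synopsis names only Groups A and B.
- A patient recorded as anti-HBs negative, on a result that may be up to a year old, has no screening quantitation.
- Nothing says what follows if the Visit 2 titre proves to be 20 or more.

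**The case against.** The strongest reply is that this is a small operational matter. The protocol expects the event to be rare, the study is exploratory with 18 patients, and a synopsis or visit table need not repeat every contingency. The turnaround is stated for screening tests, and Table 1 allows more room than section 4.7. Figure 1, which holds the study algorithm, is not shown in the text available and may carry the rule. The planned third dose already means that some patients depart from the historical two-dose schedule. How one-dose patients are analysed may also be left to a statistical analysis plan.

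Much of this limits the size of the point, but it does not supply the missing step. No passage puts a result in the staff's hands before dose 2. Table 1 does mark dose 3 as conditional, so brevity does not explain its silence on dose 2.

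Some stronger readings are tempting and are not supported:

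- **That the baseline exclusion is equally unworkable.** It is not, because known anti-HBs positives have a quantitative screening titre weeks before dose 1.
- **That a patient at 20 or more distorts the endpoint because of this timing.** The protocol knowingly admits titres below 20, so patients at 10-19 already meet the 10 mIU/mL level at entry.
- **That calling the event unlikely contradicts the rationale.** The background says "an anamnestic boost in anti-HBs has been reported in a substantial minority of immunocompetent anti-HBc positive individuals after a single dose", but this concerns immunocompetent people given traditional vaccine and states no titre. It gives no rate of reaching 300 under immunosuppression.
- **That each affected patient shifts a group's seroprotection rate by 1/6 = 16.7 points, or the overall rate by 1/18 = 5.6 points.** Those figures are only one patient's weight. A patient at 300 or more is already far above 10 mIU/mL, and nothing shows that omitting dose 2 would change that patient's status at week 24 or 60.

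**Conclusion.** The point holds for the dose-2 rule. As scheduled, the deciding sample and the dose coincide: 0 days are available by Table 1 and at most 2 days within the interval in section 4.7, against a turnaround of up to nearly 5 days. The passages also disagree on whether dose 2 is conditional at all and on its window. The regimen of a strong early responder is therefore undefined.

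The size of the effect on the endpoints cannot be given. The documents do not state how often a titre of 300 is reached after one dose, and the binary seroprotection result may not change. The geometric mean titre and the later titres could depend on whether dose 2 was given, but no figure in the documents quantifies this.

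The conclusion assumes that the week 4 assay has roughly the stated screening turnaround and that Figure 1 adds no earlier draw or deferred visit. For exclusion 2, only a clarification of wording is warranted.

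**What to change.** Reconcile section 4.7 with the Synopsis, section 4.4, section 6.7 and Table 1, including the two dose-2 windows. Either the titre that governs dose 2 is available before that dose is due, or the rule is removed. This is a clinical decision for the sponsor, and no preference is expressed here.

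If the rule stays, keep one-dose patients in the main analysis, list them separately, and show the historical comparison with and without them. Leaving them out altogether would select on response and remove the strongest responders, which would bias seroprotection and geometric mean titre downward.

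As a minor point, state for all three groups which sample governs exclusion 2.

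The cost is a short amendment and at most one earlier blood draw or assay per patient.

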5.0. TRIAL OBJECTIVES

There are two co- primary objectives: (1.) To assess immunogenicity of Heplisav-B and (2.) to assess safety in medically immunosuppressed patients. The former will require assessing the proportion of patients who respond with seroprotective levels (>10 mIU/mI) of anti-HBs and who maintain this response until study completion at week 60. The second objective will require follow up of all patients for one year after the last dose of vaccine during which time all adverse events will be collected.

6.0. TRIAL DESIGN

The study is non blinded and exploratory only.

The clinical algorithm describing the study is depicted in Figure 1. Actions taken at clinic visits is depicted in Table 1.

6.1. Primary Study Endpoints/Secondary Endpoints

Primary endpoints: determination of (1) adequate safety and (2) immunologic efficacy of Heplisav-B in patients taking ISDT. Immunologic efficacy will be determined by the seroprotection rate (SPR) or percentage of patients who have anti-HBs titers greater than 10 mIU/ml at weeks 24 and 60. Secondary endpoints include (1) determination of the percentage of patients with anti-HBs titers ≥ 100 mIU/ml at weeks 24 and 60. Both (1) and (2) as well as geometric mean titer of anti-HBs at all study visit intervals will be will be compared to those observed with historical immune competent cohorts who received identical dosing with Heplisav-B. An additional secondary endpoint will to determine the proportion of patients on ISDT who require a third dose of vaccine to induce seroprotective level of anti-HBs.

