2.0 STUDY SYNOPSIS

Title of Study:	Immunologic Efficacy of Heplisav B Vaccine in Patients Undergoing Treatment with Immunosuppressive Medications
Sponsor:	Baylor Scott and White Research Institute
Phase of Development:	Phase 1 (Medically immunosuppressed subjects)
Objectives:	Preliminary trial of Heplisav-B vaccine in medically immunosuppressed patients with co-primary objectives of vaccine immunogenicity and patient safety
Study Design:	This is an open label exploratory study of the immunologic efficacy and safety of an FDA licensed HBV vaccine that contains HsAg-1018 adjuvant which has TLR 9 agonist properties (Heplisav-B). It will be used in patients treated with long term immunosuppressive drug therapy. The patients will be given two doses of Heplisav-B, the first delivered at the baseline visit and the second at week 4. Anti-HBs titers will be determined at baseline and at weeks 4, 8, 12, 24 and 60. The proportion of those with seroprotective anti-HBs levels and the geometric mean titers of anti-HBs at each time interval will be compared with those observed in phase III trials of immunocompetent individuals receiving the same dosing schedule. Individuals who fail to demonstrate protective levels of anti-HBs at week 8 will be given a third booster dose at week 12.
Study Population:	A total of 18 patients will be entered into the study including 3 evenly sized groups of 6 as follows: Group A patients are taking tumor necrosis factor alpha or interleukin inhibitor therapy for underlying chronic inflammatory disorders; Group B patients are taking chemotherapy for solid organ malignancy; and Group C patients are either recipients of livers from anti-HBc positive donors or individuals transplanted for chronic HBV infection without recurrent hepatitis B at the time of enrollment. Serologic Characteristics Per Group: All patients in Groups A and B must be HBsAg negative but anti-HBc positive to qualify indicating that they have serologic evidence for resolved hepatitis B. Those with low titer (<20 mIU) antibody will not be specifically excluded permitting observation of a possible anamnestic anti-HBs response. Patients in Group C will have either a remote history of liver transplant for HBV or receipt of an anti-HBc positive donor liver. Eligibility requires HBsAg to be negative w/wo anti-HBc reactivity.

Safety Evaluation:	Yes
Efficacy Evaluation:	Yes

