9.0 ASSESSMENT OF EFFICACY

9.1 Efficacy Parameters

- Assessment of proportion of subjects with anti-HBs titers ≥ 10 mIU/ml at each study interval.
- Assessment of percentage of subjects with anti-HBs titers ≥ 100 mIU/ml at each study interval.

- Assessment of geometric mean titers for all subjects at each study interval.
- Assessment of reasonable safety in patients who are medically immunosuppressed

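### The primary seroprotection rate ignores baseline, so a patient who enters with anti-HBs between 10 and 20 mIU/mL and merely stays above 10 is scored as vaccine efficacy

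*Protocol*

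**What the plan says.** **Entry.** The only titre-based exclusion in section 7.2 is "Anti-HBs titer ≥ 20 mIU/mL at baseline". Section 4.6 confirms that this is deliberate: "Patients who have low titer anti-HBs at baseline (< 20 mIU) will not be excluded". The synopsis (2.0) gives the reason: "Those with low titer (<20 mIU) antibody will not be specifically excluded permitting observation of a possible anamnestic anti-HBs response".

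**Endpoint.** For weeks 24 and 60, section 6.1 states: "Immunologic efficacy will be determined by the seroprotection rate (SPR) or percentage of patients who have anti-HBs titers greater than 10 mIU/ml". Section 9.1 repeats an absolute limit with a different inequality: "Assessment of proportion of subjects with anti-HBs titers ≥ 10 mIU/ml at each study interval". Neither refers to the baseline titre.

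**Objective.** Section 5.0 is worded in terms of response: "the proportion of patients who respond with seroprotective levels", maintained to week 60. It does not define response against baseline.

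**Uses of the result.** The synopsis says that the proportions and geometric mean titres "will be compared with those observed in phase III trials of immunocompetent individuals receiving the same dosing schedule". Section 6.1 adds a secondary endpoint, the "proportion of patients on ISDT who require a third dose of vaccine to induce seroprotective level of anti-HBs".

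**Data available.** Quantitative anti-HBs is scheduled at baseline and at weeks 4, 8, 12, 24 and 60 (synopsis and Table 1).

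**The concern.** The eligible range (below 20) overlaps the success range (above 10). In the overlap, the endpoint cannot tell antibody left from past infection from antibody raised by the vaccine. The synopsis keeps low-titre patients so that an anamnestic response can be observed, and those already above 10 are the ones whose response this endpoint cannot show.

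The third-dose endpoint has the same weakness. An unchanged entrant still above 10 at week 8 is recorded as not needing a third dose, as if two doses had induced protection.

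The historical comparison is affected too. Section 4.3 describes the phase III participants as non-infected and immune competent, so they are not a matching reference for patients who start above the limit.

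Section 11.2 relies on the efficacy observations to judge whether further studies are warranted. In groups of six, one misclassified patient can change the impression given.

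**Working it through.** **Inputs from the protocol.** Groups of 6, total 18 (11.2); 12 patients in Groups A and B together. Entry below 20 (7.2). Success above 10 at weeks 24 and 60 (6.1). As many as 40% of people with the resolved-hepatitis profile are seroprotected (4.0, rationale). The share at 10 to below 20 is not given. No target rate or power is stated, so there is no planned figure to reproduce beyond 3 × 6 = 18.

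**1. Effect per patient.** Let n be the group size, m the responders with baseline below 10, b the entrants at 10 to below 20 who truly boost, and k the entrants in that band who do not respond but stay above 10.

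Crude rate = (m + k + b)/n; true responder rate = (m + b)/n; difference = k/n.

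For k = 1: 1/6 = 16.7 points, 1/12 = 8.3 points, 1/18 = 5.6 points. A patient who truly boosts adds no error.

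Hypothetical group of 6 with m = 2:

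| k | b | Crude | True |
|---|---|---|---|
| 1 | 0 | 3/6 = 50.0% | 2/6 = 33.3% |
| 2 | 0 | 4/6 = 66.7% | 2/6 = 33.3% |
| 1 | 1 | 4/6 = 66.7% | 3/6 = 50.0% |
| 0 | 2 | 4/6 = 66.7% | 4/6 = 66.7% |

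**2. How many might enter in the band (assumption).** Let x be the share of all patients with this profile who lie at 10 to below 20. Take 60% as below 10 and the remainder, 40% − x, as 20 or more and so excluded. The share among eligible patients is x/(0.60 + x).

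| x | Share of eligible | Expected among 12 in A and B |
|---|---|---|
| 0 | 0% | 0 |
| 5% | 0.05/0.65 = 7.7% | 0.9 |
| 10% | 0.10/0.70 = 14.3% | 1.7 |
| 40% | 0.40/1.00 = 40% | 4.8 |

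The last row is a bound, not a scenario: it puts every seroprotected patient in the band and none at 20 or more. All these counts are before removing patients who boost. Group C is little exposed. Section 4.0 says that anti-HBs is almost always undetectable after transplantation for hepatitis B, and section 4.6 expects recipients of anti-HBc positive livers to be seronegative.

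**3. Direction over time (assumption: exponential decay, no response).** To be above 10 at week t from baseline c, the half-life must exceed t × ln 2 / ln(c/10).

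| Baseline | Week 8 | Week 24 | Week 60 |
|---|---|---|---|
| 15 | 13.7 weeks | 41.0 weeks | 102.6 weeks |
| 19 | 8.6 weeks | 25.9 weeks | 64.8 weeks |

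From 15, a half-life of 13.7 to 41.0 weeks means no third dose at week 12 and a failure at week 24. From 41.0 to 102.6 weeks gives a success at week 24 and a failure at week 60. Above 102.6 weeks gives a success at both. Week 24 is therefore more exposed than week 60.

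**4. Cost of stratifying.** For 0 responders the exact (Clopper-Pearson) 95% upper limit is 1 − 0.025^(1/n): 45.9% for n = 6 and 60.2% for n = 4.

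**The case against.** The strongest reply is that seroprotection is by convention an absolute threshold, that low-titre patients are admitted openly, and that in an exploratory, descriptive study of 18 the serial titres would show any unchanged patient. Reporting by baseline stratum is also commonly left to a statistical analysis plan. Part of this stands: no formal test depends on the rate, and neither the geometric mean titres nor the 100 mIU/mL endpoint is distorted in this way. But the protocol itself fixes the primary endpoint and calls it immunologic efficacy. A stratified table elsewhere would not change that definition. For someone already above 10, status is not effect.

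A second reply is that non-response is only inferred. Section 4.0 reports a boost in a substantial minority of immunocompetent anti-HBc positive people, but after one dose of traditional vaccine. Here two doses of a more immunogenic vaccine are given, to immunosuppressed patients. That is fair: the protocol gives no response rate for this setting, so non-response is plausible but not quantified.

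A third reply is that any replacement rule is imperfect. A drift from 9 to 11 would count, while a rise from 15 to 25 might not. This also stands. A rule with a required rise gives the true responder rate only as far as the chosen rise separates response from fluctuation, which is why the crude rate should stay alongside it.

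A reader might infer that the seroprotection rate is bound to be inflated. The documents do not support this. The number in the band may be zero, some entrants will boost, and an unchanged entrant who misses the third dose may later count as a failure.

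**Conclusion.** The point holds as a defect in the endpoint definition. Entry below 20 and success above 10 overlap, nothing in the protocol links success to baseline, and this conflicts with the response wording of section 5.0. The size per patient is certain: 16.7 points in a group of 6, 8.3 in Groups A and B together, 5.6 in all 18. The number of such patients is unknown. The expected counts above rest on an assumed share in the band, and the timing results on assumed exponential decay from 15 or 19.

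A reader might go further and conclude that admitting low-titre patients is an error, or that the trial's immunogenicity results are invalid. Neither follows. Admission has a stated purpose, and the data needed to separate the two kinds of patient are already collected. The consequence is a potentially misleading headline rate and historical comparison in very small groups. It should be fixed.

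**What to change.** Amend sections 5.0, 6.1 and 9.1, using the baseline quantitative anti-HBs:

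- Report the seroprotection rate and the third-dose proportion separately for baseline below 10 and baseline 10 to below 20.
- In the overall responder rate, keep all patients in the denominator. Count an entrant below 10 on reaching the limit. Count an entrant at 10 to below 20 only if a rise over baseline is also met. The sponsor chooses its size and fixes it before results are seen, since a rise chosen afterwards in an open-label study would be post hoc.
- Keep the crude rate as supportive.
- Base the historical comparison on the stratum below 10. State that anti-HBc positive patients may still respond anamnestically and so differ from the non-infected phase III participants.
- Use one inequality for the rate and the baseline split. Sections 5.0 and 6.1 use above 10; section 9.1 uses 10 or more.

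The third-dose trigger is also worded inconsistently, in the synopsis, sections 4.4 and 4.7 and the Table 1 footnote. The sponsor must reconcile those places separately; nothing proposed here changes the dosing rule.

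The cost is wording: no new visits, tests or enrolment changes. The downside is a possibly lower reported rate and small strata. For 0 responders, the exact 95% interval widens from 0–45.9% with 6 patients to 0–60.2% with 4.
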